4.1.3. Secondary endpoints

a. Assessment of the diagnostic accuracy of “In-Clinic LVAT” test at M0 follow-up: Independent reviewer validation of LV threshold value provided by algorithm

This endpoint is the number of accurate determination of the pacing threshold value provided by the algorithm feature and an independent reviewer, on all LV pacing vectors and all pacing configurations available at M0 follow-up.

Diagnostic accuracy is defined as an adjudication of LV threshold value provided by the algorithm. The adjudication is based on capture and loss of capture analysis on electrogram strips recorded and stored during “In-Clinic LVAT” tests. The threshold value provided by the algorithm compared to the reviewer adjudication is considered accurate if the difference is within ± 1 step. The reason for incorrect determination of capture/loss of capture (if any) will be reported.

In case several LV Vector Tests were eligible with the same LV pacing vector, in the same pacing configuration, for the same subject, on the same follow-up, only the last one will be considered.

b. Assessment of the success rate of “In-Clinic LVAT” test at M0 follow-up: comparison to manual LV threshold tests results

This endpoint is the success rate of “In-Clinic LVAT” feature on pacing vectors and pacing configurations available at M0 follow-up. The method of analysis is similar to the primary endpoint.

c. Assessment of the success rate of “In-Clinic LVAT” test at M1 follow-up: comparison to manual LV threshold tests results

This endpoint is the success rate of “In-Clinic LVAT” feature on pacing vectors and pacing configurations available at M1 follow-up. The method of analysis is similar to the primary endpoint.

d. Evaluation of the applicability of the algorithm

The algorithm may not be applicable to some subjects, mainly because of a very long inter-ventricular conduction delay. A subject is defined as eligible as soon as one LV Vector Test is complete.

The endpoints for the applicability of the algorithm in the population are:

- The percentage of subjects who are eligible to receive the feature that is the percentage of subjects with at least one complete LV Vector Test at M0 and M1 follow-ups.
- The number of LV Vector Tests attempted, and percentage of completed and successful LV Vector Tests at M0 and M1 follow-ups per subject.

e. Assess the device characteristics in terms of safety and deficiencies

- Serious adverse device events and device deficiencies will be collected during each subject follow-up. Confirmation of absence of USADE during “In-Clinic LVAT” tests will be evaluated by analyzing all SAEs and device deficiencies collected at each follow-up.
- The focus of the “In-clinic LVAT” deficiencies will include:
 - o Assessment of pacing threshold underestimation: comparison to manual LV threshold value will be performed by comparing manual and automatic LV threshold values at each follow-up. An underestimated LV threshold value of “In-Clinic LVAT” feature is defined as a value result more than 2 steps below the LV threshold measured manually. For all the eligible complete LV Vector Tests collected, only manual LV threshold test performed in the same conditions and reported in the electronic Case Report Form (eCRF) will be retained. Only one LV Vector Test per LV pacing vector per subject will be analyzed. In case several LV Vector Tests are eligible with the same LV pacing vector, for the same subject, on the same follow-up, only the last one will be considered.
 - o Confirmation of absence of unexpected function operations by analyzing EGM and ECG performed during “In-Clinic LVAT” test at each follow-up. Any unexpected function operation will be reported.

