11. INDEPENDENT CLINICAL STUDY COMMITTEES: INDEPENDENT REVIEWER

An independent physician will review and adjudicate technical data of the LV pacing threshold value provided by the algorithm.

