4.5	3.5-5.0
4.0	3.0-5.0
3.5	2.5 - 4.5
3.0	2.25 - 4.0
2.75	2.25 -3.5
2.5	2- 3.5
2.25	1.75-3
2.0	1.5-2.5
1.75	1.25-2.25
1.5	1.0-2.0
1.25	0.75-1.75
1	0.5-1.5
0.75	0.25-1.25
0.5	0.25-1.0

LEVEA – Statistical Analysis Plan

0.25	0.25-0.75
------	-----------

Note: if an LV test is reported to be done, but no manual threshold value is present, it will be imputed as “Missing”.

- A failed LV Vector Test: threshold value provided automatically by the algorithm is not equivalent to the manual threshold test done by the physician or adjudicated by the independent reviewer among the complete LV Vector Tests.

As values determined by the algorithm are not displayed on the programmer screen, data are stored in the electronic Real-Time Data (RTD) files that are loaded in the electronic Case Report Form (eCRF) in order to be extracted by the sponsor.

- Diagnostic accuracy is defined as an accurate adjudication by an independent reviewer of LV threshold value provided by the algorithm. The adjudication is based on capture and loss of capture analysis on electrogram strips recorded and stored during “In-Clinic LVAT” tests. The LV threshold value provided by the algorithm compared to the reviewer adjudication is considered accurate if the difference is within ± 1 step.

The “Accurate” range for the Independent Reviewer for a Algorithm (Automatic) threshold is provided in the table below:

Table 5: Equivalent ranges for Accurate LV tests
(Algorithm vs. Independent reviewer)

Threshold value obtained with the algorithm (Automatic) (in V)	Accurate Range (Independent reviewer)
>5	>5
5.0	>4.5
4.5	4.0-5.0
4.0	3.5-4.5
3.5	3.0-4.0
3.0	2.5-3.5
2.5	2.25- 3
2.25	2.0-2.5
2.0	1.75-2.25
1.75	1.5-2.0

LEVEA – Statistical Analysis Plan

1.5	1.25-1.75
1.25	1.0-1.5
1.0	0.75-1.25
0.75	0.5-1.0
0.5	0.25-0.75
0.25	0.25-0.5

- Assessment of LV pacing threshold underestimation: comparison to manual LV threshold value will be performed by comparing manual and automatic LV threshold values at each visit. An underestimated LV threshold value of “In-Clinic LVAT” feature is defined as a value result more than 2 steps below the LV threshold measured manually (meaning -0.5V if threshold<2.5V, else -1V as measured).

Table 6: Ranges for Under-estimated LV tests
(Manual vs. Algorithm)

Manual Threshold value obtained (in V)	Under-estimated if - Automatic threshold value (in V)
7	< 5
6	<4.5
5	< 4.0
4.5	<3.5
4.0	<3.0
3.5	<2.5
3.0	<2.25
2.75	<2.25
2.5	<2.0
2.25	<1.75
2.0	<1.5
1.75	<1.25

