10. SECONDARY EFFICACY ANALYSES

Secondary and Ancillary endpoints will be assessed at all visits using descriptive statistics. Point estimates and exact CI (Clopper & Pearson, 1934) will be presented wherever possible.

Whenever a Statistical test is performed for a Secondary Endpoint, it is of hypothesis generating and descriptive in nature.

10.1. ASSESSMENT OF DIAGNOSTIC ACCURACY OF “IN-CLINIC LVAT” TEST AT M0 VISIT: INDEPENDENT REVIEWER VALIDATION OF LV THRESHOLD VALUE PROVIDED BY ALGORITHM

This endpoint is the number of accurate determination of the LV pacing threshold value provided by the algorithm feature and an independent reviewer, on all LV pacing vectors and all pacing configurations available at M0 visit.

Diagnostic accuracy is defined as an accurate adjudication by an independent reviewer of LV threshold value provided by the algorithm. The adjudication is based on capture and loss of capture analysis on electrogram strips recorded and stored during “In-Clinic LVAT” tests. The LV threshold value provided by the algorithm compared to the reviewer adjudication is considered accurate if the difference is within ± 1 step (meaning ± 0.25 V if threshold < 2.5V, else ± 0.5 V as measured). The definition of an Accurate LV threshold value is provided above in Table 5.

In case the algorithm and the reviewer adjudication provide both a LV threshold value equal to “>5V” (the LV vector test has resulted in “no capture” or “threshold value higher than 5V at starting amplitude), the LV threshold value is considered accurate. Number and percentages of “accurate” and “inaccurate” matches will be presented along with the exact 95% CI (Clopper & Pearson, 1934).

This analysis will be performed on M0-ITT population.

Decomposition of Diagnostic Accuracy by LV Vector and by LV pacing configuration

Total number of attempted, completed, and accurate LV vector tests will be presented by LV vector for each LV pacing configuration.

For the LV tests performed for subjects with either IS1 and IS4 leads (six LV vectors common to IS1 and IS4), the percentage for the number of LV vector tests “attempted”, will be calculated based on the number subjects implanted with either IS1 and IS4 leads.

For the LV tests performed for patients with IS4 leads (eight LV vectors pertaining only to IS4), the percentage for the number of LV vector tests “attempted”, will be calculated based on the number of patients implanted with IS4 lead.

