13. ADDITIONAL EXPLORATORY ANALYSIS

Whenever a Statistical test is performed for an Additional Analysis, it is of hypothesis generating and descriptive in nature.

13.1. ACCURATE DETERMINATION OF HIGH PACING THRESHOLD VALUE (NO CAPTURE OR >5V) : ALGORITHM Vs. INDEPENDENT REVIEWER

All LV vector tests are done at a starting amplitude of 5V for all LV pacing configurations. Therefore, if the LV threshold value is > 5 V or if there is no capture at the starting amplitude for the tested LV vector, then the algorithm identifies the LV threshold value as a high pacing threshold “> 5V”.

Number and percentage of correct determination of high pacing threshold value (>5V) provided by the algorithm feature and an independent reviewer, on all LV pacing vectors and all LV pacing configurations available at M0 visit will be presented. Percentage will be based on all subjects included in the M0-ITT.

A Fisher exact test will be performed to test the significance of association between accurate determination provided by the algorithm feature and the independent reviewer. The two-sided p-value will be presented.

In addition, the Sensitivity and Specificity as defined below will also be presented:

i. Sensitivity or Probability (Algorithm feature = High Pacing Threshold | Independent reviewer = High Pacing Threshold) = $TP/(TP+FN)$

i. Specificity or Probability (Algorithm feature = Not High Pacing Threshold | Independent reviewer = Not High Pacing Threshold) = $TN/(FP + TN)$

13.2. ASSESSMENT OF CONSISTENCY OF “IN-CLINIC LVAT” TEST BETWEEN M0 AND M1 VISITS: COMPARISON TO MANUAL LV THRESHOLD TESTS RESULTS

At each of the two subject visits, success rate will be calculated for each LV vector and each LV pacing configuration based on M0-ITT and M1-ITT respectively. As we have up to 14 LV vectors and 3 configurations, we will have a total of 42 success rates at each M0 and M1 visits.

Null Hypothesis: The Success-rate for LV tests at M0 visit = The success rate for LV tests at M1 visit

LEVEA – Statistical Analysis Plan

Alternative Hypothesis: The Success-rate for LV tests at M0 visit \neq The success-rate for LV tests at M1 visit.

A paired t-test will be performed to test if the mean difference of the success rate over the two visits is significantly different from 0. A two-sided p-value will be presented. This will be performed by configuration and overall. The mean difference and its 95% CI will also be presented.

This analysis will be performed on ITT.

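### Neither the CIP nor the SAP masks the independent reviewer to the algorithm's threshold, so the design permits anchoring in the diagnostic-accuracy reference

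*Protocol*

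**What the plan says.** The first secondary endpoint is the independent reviewer's validation, at M0, of the threshold produced by the algorithm. CIP 4.1.3 a states: "Diagnostic accuracy is defined as an adjudication of LV threshold value provided by the algorithm". CIP 11 gives the reviewer's role in one sentence: "An independent physician will review and adjudicate technical data of the LV pacing threshold value provided by the algorithm". SAP 10.1 keeps the definition and names the reader: "Diagnostic accuracy is defined as an accurate adjudication by an independent reviewer of LV threshold value provided by the algorithm". SAP 5.7 carries the same definition.

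The method is described only in outline. "The adjudication is based on capture and loss of capture analysis on electrogram strips recorded and stored during" the automatic test. The comparison rule follows: "The threshold value provided by the algorithm compared to the reviewer adjudication is considered accurate if the difference is within" ±1 step.

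SAP Table 5 lists an accepted reviewer range for each algorithm value; for example, an algorithm value of 2.0 V is accurate if the reviewer reads 1.75–2.25 V. SAP 13.1 conditions on the reviewer's result, with sensitivity defined as the probability of ("Algorithm feature = High Pacing Threshold | Independent reviewer = High Pacing Threshold").

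**The concern.** The reviewer serves as the reference standard for the algorithm, yet the task is worded as adjudicating the algorithm's own answer. A reader who knows the index result can drift towards it when a beat is hard to classify. CIP 7.1 lists fusion and anodic stimulation among its main risks, and such beats are plausible examples.

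This endpoint is a valuable check on the algorithm. It uses the strips from the automatic test itself, so threshold variability between two separate tests does not enter. Its tolerance is ±1 step, against ±2 steps for the manual comparison. If the reference leans towards the value under test, much of that advantage is lost. The comparator figures tabulated in CIP 2.2.1 d run from 95% to 99.7%, so even a shift of a point or two could change how the LEVEA result reads beside them.

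**Working it through.** **1. Is masking or reading order stated anywhere?** CIP 4.1.3 a, CIP 11, SAP 5.7 and SAP 10.1 all make the algorithm's value the object of adjudication. None mentions masking, a reading order, an independent first value or a lock. The manual comparison is treated differently: CIP 6.1.2 and 6.1.3 place the manual tests before the automatic one to limit bias. CIP 4.1.1 and SAP 5.7 say that algorithm values are not shown on the programmer screen, while CIP 5.4 says that results are displayed there. Either way, this concerns site staff and does not protect the reviewer.

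**2. Does the reviewer produce a separate threshold?** The rules imply so. A ±1 step difference, the ranges in Table 5, the SAP 10.1 rule for both sources giving >5 V, and the two-way classification in SAP 13.1 all need a reviewer value. But a value can be recorded separately and still be recorded with the algorithm's answer in view.

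**3. Could the value reach the reviewer?** SAP 5.7 and 17.8 store algorithm values in the RTD files, and SAP 11.1 C says that electrograms are collected in the RTD files too. No step is described that removes the value before the strips are read.

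**4. Direction of bias.** Suppose anchoring turns a disagreement into agreement.
- A false negative becomes a true negative. FN falls, so TP/(TP+FN) rises; TN rises, so TN/(FP+TN) does not fall.
- A false positive becomes a true positive. FP falls, so specificity rises; TP rises, so sensitivity does not fall.

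Accuracy rises in both cases.

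**5. Size.** The plan gives no expected rate, goal or sample size for this endpoint, so there is no planned figure to reproduce. Let d be the true disagreement rate and s the share of disagreements that anchoring converts. Both are assumptions.

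Reported disagreement = d(1 − s); inflation of accuracy = d × s.

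The nearest disagreement figures in the documents are:
- CIP 2.2.1 c, a similar feature against a core laboratory: 233 of 234 matched, so 1/234 = 0.4%.
- CIP 2.2.2, the preliminary algorithm against experts: 113/115 and 202/204, so 2/115 = 1.7% and 2/204 = 1.0%.

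These support d of roughly 1–2%. The value d = 6% is a less favourable case with no source in the documents.

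| d | True accuracy | Reported, s = 0.25 | Reported, s = 0.50 | Reported, s = 0.75 | Inflation (points) |
|---|---|---|---|---|---|
| 1% | 99% | 99.25% | 99.5% | 99.75% | 0.25–0.75 |
| 2% | 98% | 98.5% | 99.0% | 99.5% | 0.5–1.5 |
| 6% | 94% | 95.5% | 97.0% | 98.5% | 1.5–4.5 |

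**6. Primary endpoint.** CIP 4.1.2 and SAP 9.1.2 judge success against the manual value. The sample size reproduces: with n = 231 and success at 217 or more, the exact one-sided alpha at 90% is 0.0239 and the power at 95% is 0.816. Then 231/5 = 46.2, rounded up to 47, and 47/0.8 = 58.75, rounded up to 59. None of these figures involves the reviewer.

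**The case against.** The strongest reply is that silence is not evidence of an unmasked read. A reader might infer from the definition that the reviewer sees the algorithm's value first and that the endpoint is in fact anchored. The documents do not say so, and the strip-based method, the ±1 step rule, Table 5 and SAP 13.1 all point to a reviewer threshold derived from the electrograms. That part of the reply stands.

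Two further inferences also fail:
- CIP 4.1.3 a requires the reason for an incorrect determination to be reported. This does not show that the reviewer knew the result while reading: the text does not say who assigns the reason or when, and it can be done after a masked read.
- This is not the only endpoint free of the manual value. The percentage of subjects with a complete test, unexpected function operations, device deficiencies and the right ventricular analysis do not use it either.

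The link to CIP 7.1 is also limited. Under-estimation of the threshold is assessed against the manual value (CIP 4.1.3 e, SAP Table 6), so masking the reviewer would not change that assessment.

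On size, the figures nearest to hand imply a small bias. That is fair, though the documents do not say whether the readers behind those figures were masked. Finally, a reading procedure could exist in the Investigator's Brochure or in the extraction document cited in SAP 17.8, neither of which is available here.

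None of this supplies a masking rule in the CIP or SAP.

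**Conclusion.** The point holds as a gap in the design, not as a demonstrated bias. The reviewer is the reference for accuracy, sensitivity and specificity, and a reviewer who already knows the algorithm's value would be complying with the plan. Anchoring therefore cannot be excluded, and under the model above its direction is upward.

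The likely inflation of accuracy is 0.25 to 1.5 points if true disagreement is 1–2%, and 1.5 to 4.5 points if it is 6%, in each case with s between 0.25 and 0.75. These ranges assume that anchoring only turns disagreement into agreement; the documents give no value for s.

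The consequence is limited to a descriptive secondary endpoint (CIP 8.5.2, SAP 10.1) and an exploratory analysis (SAP 13.1). No hypothesis test of the primary endpoint and no sample-size figure depends on it.

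**What to change.** State the reading procedure in CIP 4.1.3 a, CIP 11 and SAP 10.1:

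1. The reviewer first receives the electrogram strips without the algorithm value, the manual value or site comments. The reviewer records a threshold, or >5 V, or not readable. This entry is locked.
2. The ±1 step comparison in Table 5 and the sensitivity and specificity in SAP 13.1 are computed by program from the locked reading only.
3. The algorithm value is revealed afterwards, solely to assign the reason for a disagreement.

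If the read is already done this way, the added text simply documents it. The cost is a revised reviewer form and a lock step, with the same reviewer and the same strips. This is a cheap improvement.

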4.1.4. Ancillary endpoint

Right ventricular pacing electrograms might be collected and analyzed to identify right ventricular capture and non-capture beats and to assess a right ventricular threshold determination method on Platinium Implantable Cardioverter Device (ICD).

4.2. NUMBER OF SUBJECTS/SITES

59 subjects should be included in approximately 12 sites in Europe.

4.3. STUDY DURATION

Each subject will participate in the study for maximum 3 months.

As the study plans an inclusion period of approximately 3 months, the study duration is approximately 6 months.

The Sponsor may perform adjustments/enhancements to the study CIP or eCRF as deemed appropriate in order to guarantee consistency to the main study endpoints. Whenever relevant and required, the EC and the Competent Authorities (CA) shall be notified by the investigator about any change made to the study.

4.4. INCLUSION CRITERIA

Subjects must meet all of the following criteria to be considered for enrollment:

- Subject already implanted (de-novo, upgrade or replacement) according to the relevant ESC Guidelines [1]:
 - With IS1 Platinium SonR CRT-D (models 1811, 1841, CE-marked) for maximum of 5 days or;
 - With IS4 Platinium SonR CRT-D (model 1844, CE-marked).
- Right atrial, right and left ventricular leads must be implanted. Only bipolar and quadripolar for Left Ventricular lead.
- Reviewed, signed and dated informed consent.

4.5. EXCLUSION CRITERIA

Subjects who meet any of the following criteria are not eligible to be enrolled in the study:

- Subject included in another clinical study that could confound the results of this study;
- Malfunction or dislodgment of right atrial, right and left ventricular implanted leads;
- Subject diagnosed with permanent atrial fibrillation;
- Known pregnancy;
- Minor age;
- Under protection or guardianship;
- Unavailability for scheduled follow-up or refusal to cooperate.

A subject will be considered eligible to be enrolled in the study when the Informed Consent has been completed and the subject satisfies all the inclusion and exclusion criteria. Individuals who are screened but do not satisfy the inclusion and exclusion criteria will not be considered enrolled in the study. Logs will be maintained for screening and consenting subjects.

5. INVESTIGATIONAL DEVICE INFORMATION

5.1. DEVICE DESCRIPTION

5.1.1. Feature under investigation

The feature under investigation is the “In-Clinic LVAT” Test.

It is a non CE-marked software function, embedded in Platinium SonR CRT-D devices and it is intended to be used only under medical supervision during subject follow-up by activating the function with dedicated clinical software of the programmer.

This feature is embedded in Platinium SonR CRT-D devices equipped with software version 2.4.2 (or upgraded version).

5.1.2. Associated device not under investigation

Platinium SonR CRT-D devices (models 1811, 1841, 1844) are triple chamber implantable cardioverter defibrillators CE-marked, designed to perform standard pacing and sensing functions.

The embedded software is CE-marked, similar to the commercial version with an unlocked non CE-marked function, the “In-Clinic LVAT” test.

The considered models are:

Platinum device	RV-LV leads		
	DF1-IS1	DF4-IS1	DF4-IS4
SonR CRT-D model	1811	1841	1844

5.1.3. *Implantable leads*

Any market approved right atrial (A) implantable lead, right ventricular (RV) cardioversion/defibrillation lead DF1 or DF4 and left ventricular (LV) implantable IS-1 or IS-4 lead (only bipolar and quadripolar) could be used as long as there is no malfunction and the leads integrity are preserved.

5.1.4. *Orchestra Plus Programmer*

In order to launch “In-Clinic LVAT” feature, an Orchestra plus programmer with the 2.54.C1 (or upgraded version) clinical SmartView version will be used.

This system is capable to launch:

- all available functions of the SmartView 2.54 commercial version (or upgraded version),
- “In-Clinic LVAT” tests.

5.2. DEVICE TRACEABILITY

[figure not shown]
Devices will be used according to the physician’s manual, to the clinical practice, and to the CIP.

To ensure traceability throughout the study, the serial number assigned to Platinum SonR CRT-D device, and the programmer will be documented in the device accountability log at the site level, with the following information:

- Subject identification Platinum SonR CRT-D model & serial number,
- Programmer serial number installed with 2.54 C1 software version (or upgraded version).

